5.6.1. MMRM

All PRO assessments will be included for this analysis. The analysis will be based on observed data, i.e., data collected at each timepoint without carrying forward previous values. Data from a limited number of PRO assessments may be used in case of substantial dropout (i.e., analysis will be limited to timepoints at which at least 10% of patients have non-missing data in both treatment groups).

The response variable will be the change from baseline to each PRO assessment. The model will include the treatment arm (ziltivekimab vs. placebo) and timepoint (Week 5, Week 13, and week 24) as fixed-effect categorical factors, the baseline PRO score and stratification factors (baseline haemoglobin (≥ 11 or < 11 g/dL) and CKD stage (3, 4 or 5)), as well as the baseline PRO score x time and treatment x time interactions. Both main effects and the interaction terms will remain in the model, regardless of significance. The model will present least squares (LS) mean estimates for each dose, least squares mean differences of each study drug dose from placebo, standard errors, 95% CIs and p-values (where applicable) for mean changes from baseline to each visit. A plot of the LS means accompanied by the 95% CI will be produced.

In addition, an overall adjusted mean estimate will be derived that will estimate the average change from baseline across all time points, giving each visit equal weight.

The standardized mean difference (SMD) including 95% CI (Hedges' g) will also be provided.

The MMRM analysis will be conducted using PROC MIXED in SAS. The model will assume unstructured covariance among the within-patient repeated measurements. If the algorithm does not converge, a heterogeneous Toeplitz (the TOEPH option in SAS PROC MIXED) will be tried first and then AR(1) as a covariance structure to achieve convergence. The Kenward-Roger approximation will be used to estimate denominator degrees of freedom.

Variables listed as categorical in the list above will be included in the CLASS statement of the procedure. The unique patient identifier will also be included as a class variable. A REPEATED statement over the visits will be included with the unique patient identifier as the SUBJECT variable in the REPEATED statement.

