5.6.2. PMM

Change from baseline in PRO domain and overall scores may be further analyzed using a pattern-mixture model using sequential modelling with multiple imputation as described by O'Kelly (O'Kelly & Ratitch, 2014), depending on exploration of the amount of missing data at post-baseline assessments, as described in Section 5.9.2.

Document: \\ieedc-vnasc01\Sites\[\]\NLHOF\IntProjects\Consulting\Projects\Corvidia\[\]
Biostatistics\01.Documentation\02.SAPI Corvidia_RESCUE_PROSAP_v2.0_21JUL2020
Author: \[\] Version No: v.2.0
Template No.: \[\] Version Date: 21JUL2020
Effective Date: 01Dec2018 Reference: \[\]

The results from this analysis will be used to judge the validity of the MAR assumption. Similar conclusions from MMRM and PMM would suggest that the results are not overly dependent on the assumptions of the primary analysis with regard to the missing data.

The sensitivity analysis will consider dropout reasons while imputing missing values after the discontinuation. Subjects who discontinued due to lack of efficacy or adverse events in the active arms are assumed to have no treatment effect after the discontinuation. These subjects are assumed to copy the profile in the placebo arm, and missing values are imputed based on the distribution estimated from the placebo group under the missing not at random (MNAR), using copy-reference approach. The rest of missing values in the placebo arm and active arms will be imputed using the observed data in their respective group under the MAR assumption. This includes the patients who were early terminated due to the impact of the Coronavirus Disease 2019 (COVID19) pandemic. The multiple imputation model will include factors such as treatment arm, baseline hemoglobin category, and CKD stage, in addition to the data outcomes at each visit.

The following steps will be performed:

Step 1 Intermittent (non-monotone) missing data will be imputed using the MCMC option of SAS PROC MI (using seed=5414).

Step 2 For monotone missing data, the values for each pattern will be imputed via the chained equation method with range restriction, using SAS PROC MI option MONOTONE REG () .

Under step 2, missing values for subjects who discontinued due to lack of efficacy or adverse events will be imputed under MNAR assumption using copy-reference approach, and missing values for subjects who discontinued due to reasons other than lack of efficacy or adverse events will be imputed under the MAR assumption.

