3.4.1 Primary Efficacy Endpoint

Primary Analysis

The primary analysis variable is the difference in percent change in hs-CRP levels from baseline (average of the hs-CRP value prior to randomization and Day 1) to the Week 13 between each active group and placebo.

The primary efficacy analysis will be carried out using a mixed model for repeated measures (MMRM) to evaluate percent change in hs-CRP levels from baseline in the ITT populations. The MMRM model will include percent change in hs-CRP from baseline as the dependent or response variable, variables for baseline hemoglobin (≥ 11 or < 11 g/dL), CKD Stage (3, 4 or 5), treatment group, visit and treatment group-by-visit interaction as categorical fixed effects, baseline value and baseline-by-visit interaction will be included as covariates. Restricted Maximum Likelihood (REML) method will be used.

The sample SAS code can be found below:

```
*****
*Note: PCHG = Percent change in hs-CRP from baseline
*      HGB = Baseline Hemoglobin category (>=11 or <11g/dL)
*      CKD = CKD Stage (3, or 4/5)
*      TRT = Treatment group
*      VISIT = Analysis visit
*      TRT*VISIT = Treatment group by visit interaction
*      BASE = Baseline value
*      BASE*VISIT = Baseline by visit interaction
*      USUBJID = Unique subject identifier
*****;
proc mixed data=efficacy method=reml covtest;
  class HGB CKD TRT VISIT;
  model PCHG = HGB CKD TRT VISIT TRT*VISIT BASE BASE*VISIT/
    DDFM=KENWARDROGER;
  repeated / type=un subject=USUBJID;
  ODS OUTPUT LSMeans=lsmeantable Diffs=LSDiffs;
run;
```

The treatment difference in terms of mean percent change from baseline will be estimated and tested in this MMRM model. The least squares means for each dose, the least squares mean differences from placebo along with the 95% confidence intervals (CIs) and p-values will be presented from the above results.

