Normality assessment for the primary efficacy variable will be performed using the Shapiro-Wilk test. Normality test will be performed on the model residuals. If substantial deviation from assumption of normality is encountered (Shapiro-Wilk p-value < 0.01), a nonparametric analysis will be performed. Median and quartiles will be presented for hs-CRP values at baseline, Week 13, and percent change in hs-CRP from baseline to Week 13. The Hodges-Lehmann estimator of the location shift between each treatment arm and placebo will be presented. The asymptotic 95% confidence limits for the location shift and p-value from the Wilcoxon test will also be presented. The nonparametric analysis will account for the covariates baseline hemoglobin (≥ 11 or < 11 g/dL) and CKD Stage (3, 4 or 5) by aligning responses within each stratum defined by the covariates prior to analysis.

The SAS code for Hodges-Lehmann estimates is listed below:

```
proc npar1way hl alpha=.05 align=strata(hl);  
  class TRT;  
  strata HGB CKD;  
  var PCHG;  
  ods output wilcoxontest=WILT hodgeslehmann=HL1;  
  run;
```

Sensitivity Analyses

Sensitivity analyses will be performed on the PP analysis population with the same method used to analyze the primary efficacy endpoint. In addition, a sensitivity analysis will be performed on the ITT analysis population using a pattern-mixture model using sequential modeling with multiple imputation to assess the robustness of the primary MMRM results to the possible violation of the missing-at-random (MAR) assumption. The sensitivity analysis will consider dropout reasons while imputing missing values after the discontinuation. Subjects who discontinued due to lack of efficacy or adverse events in the active arms are assumed to have no treatment effect after the discontinuation. These subjects are assumed to copy the profile of placebo arm and missing values are imputed based on the distribution estimated from the placebo group under the missing not at random (MNAR) using copy-reference approach. The rest of missing values in the placebo arm and active arms will be imputed using the observed data in their respective group under the MAR assumption. The multiple imputation model will include factors such as treatment arm, baseline hemoglobin category and CKD stage in addition to the data outcomes at each visit.

The following steps will be performed:

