Step 1 Intermittent (non-monotone) missing data will be imputed using the MCMC option of SAS PROC MI (using seed=5414).

Step 2 For monotone missing data, the values for each pattern will be imputed via the chained equation method with range restriction, using SAS PROC MI option MONOTONE REG ().

Under step 2, missing values for subjects who discontinued due to lack of efficacy or adverse events will be imputed under MNAR assumption using copy-reference approach, and missing values for subjects who discontinued due to reasons other than lack of efficacy or adverse events will be imputed under the MAR assumption.

These two steps will be carried out sequentially to construct 100 hypothetical complete data sets.

An ANCOVA model (not repeated measures, and with no random effects) with the following covariates will be performed for each imputation using the SAS Mixed procedure:

- HGB = Baseline Hemoglobin category (≥ 11 or < 11 g/dL)
- CKD = CKD Stage (3, or 4/5)
- TRT = Treatment group
- BASE = Baseline hemoglobin value

The SAS MIAnalyze procedure will be used to combine the results of these analyses for the imputations. The overall least square means, standard errors, 95% confidence intervals, and p-values will be reported.

Reasons for subject discontinuation that are identified as lack of efficacy will be discussed and finalized prior to database lock.

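### The ANCOVA in the pattern-mixture sensitivity analysis enters baseline haemoglobin twice and leaves out the analysed outcome's own baseline

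*SAP*

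**What the plan says.** **Sensitivity model.** Clinical SAP 3.4.1 (Sensitivity Analyses) multiply imputes the missing data and fits a single-visit ANCOVA to each of 100 completed data sets. It lists four covariates: "HGB = Baseline Hemoglobin category (≥ 11 or < 11 g/dL"), CKD stage, treatment group, and "BASE = Baseline hemoglobin value". Section 5.6.2 of the PRO SAP carries the same list, in v1.0 and v2.0.

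**Models it is meant to check.** The primary MMRM in clinical SAP 3.4.1 has the response "PCHG = Percent change in hs-CRP from baseline". Its text states that "baseline value and baseline-by-visit interaction will be included as covariates", and its sample code defines "BASE = Baseline value". The PRO MMRM (PRO SAP v2.0, 5.6.1) includes "the baseline PRO score and stratification factors".

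**Purpose.** The clinical SAP says the pattern-mixture analysis is there "to assess the robustness of the primary MMRM results to the possible violation of the missing-at-random (MAR) assumption". PRO SAP v2.0 section 5.6.2 adds an interpretive rule: "Similar conclusions from MMRM and PMM would suggest that the results are not overly dependent on the assumptions of the primary analysis".

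**The plan's other ANCOVA.** Clinical SAP section 5 sets out the End of Treatment analysis adopted after dosing stopped. There BASE is the baseline of the efficacy parameter analysed, with baseline hs-CRP as a further covariate.

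**The concern.** A missing-data sensitivity analysis is easiest to read when the missing-data assumption is what changes. Here the adjustment set changes as well: the outcome's baseline goes out and a second haemoglobin term comes in. The two analyses can then disagree because the arms happened to differ at baseline, or because one has the larger residual variance, even if no value is missing. In the other direction, such a shift could offset a real effect of the missing-data assumption and make the results look falsely alike.

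The PRO scores are more exposed than hs-CRP. They have no planned effect size, and with more than 120 patients not completing treatment the PRO SAP expects many to lack Week 24 data. Clinical SAP 3.4.2 handles the secondary endpoints in the same way as the primary, so the definition may reach them too.

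**Working it through.** **1. The plan's own figure.** Clinical SAP 2.2.4 gives a difference of -60.74 percentage points, SD 16.893, 54 per group and two-sided alpha 0.05.
- SE = 16.893 × √(2/54) = 3.25.
- Noncentrality = 60.74 / 3.25 = 18.7 on 106 df, so power is 1.000. This agrees with the stated figure of more than 99%.
- 54 / (1 - 0.10) = 60 per group, as stated.

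Neither figure depends on the covariate at issue.

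**2. Covariates side by side.**

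| Model | Haemoglobin category | CKD | Treatment | Outcome's own baseline | Continuous haemoglobin |
|---|---|---|---|---|---|
| Primary MMRM (clinical SAP 3.4.1) | yes | yes | yes | yes, also by visit | no |
| PRO MMRM (PRO SAP 5.6.1) | yes | yes | yes | yes, also by time | no |
| End of Treatment ANCOVA (clinical SAP 5) | yes | yes | yes | yes | no |
| Pattern-mixture ANCOVA (clinical SAP 3.4.1, PRO SAP 5.6.2) | yes | yes | yes | **no** | **yes** |

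The last row is the exception, and no reason is given for it.

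**3. PRO change scores.** Let s² be the variance at each time and ρ the baseline/follow-up correlation. The documents give no ρ; 0.5 to 0.7 is assumed.
- Variance of the change without baseline adjustment: 2s²(1 - ρ).
- Residual variance with baseline adjustment: s²(1 - ρ²).
- Ratio: 2/(1 + ρ) = 1.33, 1.25 and 1.18 at ρ = 0.5, 0.6 and 0.7.
- SE ratio, the square root: about 1.15, 1.12 and 1.08.
- If the arms differ by d at baseline, (1 - ρ)d is left uncorrected: 0.5d at ρ = 0.5 and 0.3d at ρ = 0.7. This is conditional on the d that occurs and averages to zero over randomisations.

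**4. Percent change in hs-CRP.** The formulas in step 3 do not apply to a percent change. Let r be the correlation of baseline with percent change, assumed to lie between 0.1 and 0.7. Omitting the baseline multiplies the SE by 1/√(1 - r²). A simulation with **complete data** checked this: 4,000 runs per r, 54 per arm, SD 16.893, true difference -60.74, haemoglobin unrelated to the outcome. Each run fitted the ANCOVA once with the outcome's baseline and once with the haemoglobin value.

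| r | 1/√(1 - r²) | Simulated SE ratio | Mean shift in estimate (points) | SD of shift (points) |
|---|---|---|---|---|
| 0.1 | 1.005 | 1.005 | 0.007 | 0.56 |
| 0.3 | 1.048 | 1.048 | 0.009 | 1.07 |
| 0.5 | 1.155 | 1.155 | -0.052 | 1.71 |
| 0.7 | 1.400 | 1.399 | -0.014 | 2.34 |

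The mean shift is essentially zero. The shift within a single trial is not, although nothing is missing.

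**5. Effect on the hs-CRP conclusion.** Even with the SE from step 1 multiplied by 1.40, the planned ratio is 60.74 / (1.40 × 3.25) = 13.3. The conclusion stands.

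**The case against.** Several counter-arguments carry weight.

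- **Only a supportive analysis is affected.** The primary MMRM is correctly specified. In the PRO SAP the pattern-mixture analysis is optional and sits within exploratory work without multiplicity adjustment. This stands and limits the severity.
- **There is no bias on average, and at the low end of the assumed range the loss is negligible.** This stands.
- **It is evidently a drafting slip.** BASE means the outcome's baseline everywhere else in the clinical SAP. That shows what was probably meant, but the wording is explicit and repeated across documents, and a programmer following it would fit the wrong model.
- **The MMRM may not be the final word for hs-CRP.** If the Shapiro-Wilk p-value is below 0.01, clinical SAP 3.4.1 moves to a Hodges-Lehmann/Wilcoxon analysis aligned on haemoglobin and CKD strata, without baseline hs-CRP. The contrast is then weaker, but only in that event and only for endpoints handled that way.
- **Correcting BASE does not make the two analyses differ only in the missing-data assumption.** They would still differ in repeated-measures versus single-visit modelling, in the baseline-by-visit term, and in likelihood versus imputation. This stands, and is why a MAR-only reference is suggested.

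A reader might also infer that the imputation model omits the outcome's baseline. The documents do not establish that: the list of imputation factors is open-ended and includes the outcomes at each visit, and Baseline is itself an analysis visit in clinical SAP 3.1.2.

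**Conclusion.** The text is wrong as written in clinical SAP 3.4.1 and PRO SAP 5.6.2, and nothing elsewhere repairs it. The consequence is lost precision and uncorrected chance imbalance in the sensitivity analysis, at the sizes shown above. Those sizes rest on assumed correlations and, for hs-CRP, on haemoglobin being unrelated to the outcome.

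Two stronger readings should be resisted. One is that the sensitivity analysis is biased: under randomisation it is not, on average. The other is that the hs-CRP finding is at risk: at the planned effect it is not. The exposure is mainly in the PRO scores, where an MMRM-versus-pattern-mixture difference, or its absence, is to be read as evidence about MAR. Severity: should-fix.

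**What to change.** 1. In clinical SAP 3.4.1 (Sensitivity Analyses), define BASE as the baseline value of the endpoint analysed: baseline hs-CRP for the primary.
2. In PRO SAP 5.6.2, define BASE as the baseline score of the PRO analysed.
3. In both, keep the haemoglobin category as the stratum factor in place of the continuous value, so that the covariates match the MMRM.
4. For clarity, name the outcome's baseline in the imputation model.
5. Fit the same ANCOVA to data imputed under MAR throughout, and use it as the reference for the pattern-mixture result. Only the missing-data assumption then differs between the two.

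Items 1 to 3 are a short correction to the covariate list in each SAP and need no new data. Item 4 is a clarification. Item 5 needs a small amount of extra programming. All should be settled before the analysis is programmed.

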3.4.2 Secondary Efficacy Endpoints

The secondary analysis variables will be summarized and analyzed in the same manner as the primary analysis variable (Section [3.4.1](#)). Each MMRM model will use change or percent change from baseline variable as applicable as the dependent or response variable.

The following secondary variables will be analyzed:

- Difference in percent change in SAA from Baseline to Week 13 between each active group and placebo.
- Difference in percent change in fibrinogen from baseline to Week 13 between each active group and placebo.

3.4.3 Exploratory Efficacy Endpoints

The following exploratory analysis variables will be summarized in the same manner as the primary analysis of the primary efficacy endpoint for the continuous efficacy endpoints.

For binary endpoints (proportions), differences in proportions and 95% CIs will be based on the normal approximation to binomials.

The sample SAS code for normal approximation for binary endpoints can be found below:

```
*****;  
*Note: ACHIEVE = status of patients achieving endpoint (1 if Yes, 2 if No)  
*      TRT = Treatment Group  
*****;  
proc freq data=endpoint;  
  by TRT;  
  tables ACHIEVE / binomial (Wald exact);  
  ods output BinomialCLs=CL BinomialProp=Proportion;  
run;
```

The following exploratory endpoints will be analyzed:

- Difference in percent change in hs-CRP levels from baseline to End of Treatment (weeks 23 through 24) between each active group and placebo.
- Difference in percent change in serum NT-pro-BNP from Baseline (average of NT-pro-BNP value prior to randomization and Day 1) to Week 13 and to End of Treatment (Weeks 23 through 24) between each active group and placebo.
- Difference in change in SAA from Baseline to End of Treatment (Weeks 23 through 24) between each active group and placebo.
- Difference in percent change in fibrinogen from Baseline to End of Treatment (Week 24) between each active group and placebo.
- Difference in change in hemoglobin from Baseline (average of the two most recent hemoglobin values prior to randomization and Day 1) to Week 13 and to End of Treatment (Weeks 23 through 24) between each active group and placebo.

- Difference in change in serum albumin from Baseline (average of the two most recent serum albumin values prior to randomization and Day 1) to Week 13 and to End of Treatment (Weeks 23 through 24) between each active group and placebo.
- Proportion of patients achieving hs-CRP response at Week 13 and to End of Treatment (Weeks 23 through 24), defined as hs-CRP <2.0 mg/L in each active group and placebo.
- Difference in change in ST2 from Baseline to Week 13 to End of Treatment (Week 24) between each active group and placebo.
- Difference in percent change in Lp (a) from Baseline to Week 13 and to End of Treatment (Weeks 23 through 24) between each active group and placebo.
- Difference in percent change in LDL-C, triglycerides, ApoB, ApoA1, ApoB/ApoA1, and lipid profile by NMR spectroscopy from Baseline to Week 13 and to the End of Treatment (Weeks 23 through 24) between each active group and placebo.
- Difference in change of creatinine based eGFR and cystatin C-based eGFR from Baseline to Week 13 and to the End of Treatment (Weeks 23 through 24) between active group and placebo.
- Difference in change of UACR from Baseline to Week 13 and to the End of Treatment (Weeks 23 through 24) between active group and placebo.
- Difference in change of the total fatigue score (PROMIS Fatigue 13a short form and selected items from the PROMIS fatigue item bank) from Baseline to Week 13 and to End of Treatment (Weeks 23 through 24) between each active group and placebo.
- Difference in change of the PROMIS interest in sexual activity item from Baseline to Week 13 and to End of Treatment (Week 24) between each active group and placebo.
- Difference in change of the Corvidia ePRO items from Baseline to Week 12 and to End of Treatment (Weeks 23 through 24) between each active group and placebo.
- Difference in change of the PGIS index from Baseline to Week 12 and to End of Treatment (Week 24) between each active group and placebo.
- Descriptive analyses of the PGIC index at Weeks 5, 13, and End of Treatment (Week 24) in each active group and placebo.
- Difference in change of the Optum SF-36 v2® Health Survey physical component summary (PCS), mental component summary (MCS) and domain scores from Baseline to Week 13 and to End of Treatment (Weeks 23 through 24) between each active group and placebo.
- Difference in change of the EQ-5D-5L index from Baseline to Week 12 and to End of Treatment (Week 24) between each active group and placebo.
- Evaluation of the psychometric properties of the PROMIS Fatigue 13a short form and selected items from the PROMIS Fatigue item bank and the Corvidia ePRO items in CKD patients – to be described in a PRO psychometric analysis plan.
- Descriptive analyses by dose and treatment may be conducted on samples stored for analysis of exploratory biomarkers, genomic and transcriptomic analysis.
- Difference in change in TSAT from Baseline to peak level, Week 13, and the End of Treatment (Weeks 23 through 24), between each active group and placebo.

- Difference in change in CHr from Baseline to peak level, Week 13, and to End of Treatment (Week 24) between each active group and placebo.
- Difference in change in TIBC from Baseline to Week 13 and to End of Treatment (Weeks 23 through 24) between each active group and placebo.
- Difference in change in serum ferritin from Baseline to Week 13 and to End of Treatment (Weeks 23 through 24) between each active group and placebo.
- Difference in change in serum iron from Baseline to Week 13 and to End of Treatment (Weeks 23 through 24) between each active group and placebo.
- Difference in change in serum hepcidin from Baseline to Weeks 13 and to End of Treatment (Week 24) between each active group and placebo.
- Difference in percent change in serum NT-pro-BNP from Baseline to Week 13 and to End of Treatment (Weeks 23 through 24) between each active group and placebo in patients with baseline NT-pro-BNP > 250 pg/mL.
- Difference in change in hemoglobin from Baseline (average of the two most recent hemoglobin values prior to randomization and Day 1) to Week 13 and to End of Treatment (Weeks 23 through 24) between each active group and placebo in patients with baseline hemoglobin < 11 g/dL.
- Difference in change in serum albumin from Baseline (average of the two most recent serum albumin values prior to randomization and Day 1) to Week 13 and to End of Treatment (Weeks 23 through 24) between each active group and placebo in patients with baseline albumin < 4.0 g/dL.

For the above efficacy variables, the observed values, changes from baseline, and percent changes from baseline (as applicable) will be summarized by treatment group using descriptive statistics using ITT.

For PROMIS fatigue 13a short form, the observed value and change from baseline in total fatigue score will be summarized by treatment at each visit.

For PROMIS SexFS, the observed value and the change from baseline will be summarized by treatment at each visit..

The PCS, MCS, and domain scores from the Optum SF-36 v2® Health Survey will only be analyzed descriptively. The observed value and change from baseline in total Optum SF-36 v2® Health Survey score will be summarized by treatment at each visit.

Psychometric analyses will be conducted using the trial data to assess the psychometric properties of the CARES Corvidia ePRO instrument. The structural validity of CARES Corvidia ePRO instrument will be evaluated by means of exploratory factor analysis. A total summary scale or set of scales will be proposed in light of the factor loadings as well as clinical and conceptual considerations. Additional details will be described in the PAP. The score(s) developed as psychometrically sound will be used to evaluate efficacy.

Descriptive analyses of the EQ-5D-5L results will be presented. Number and percentage of patients with each of five levels (no problems, slight problems, moderate problems, severe problems, and extreme problems) of response in each domain will be presented by treatment and visit. The observed value and change from baseline on the EQ-5D-5L VAS score will be summarized by treatment at each analysis visit.

Additional exploratory analyses including descriptive summaries and inferential statistics for the following will be described in a separate PRO Statistical Analysis Plan (PRO SAP): CARES Corvidia ePRO, SF-36 v2 Health Survey and derived scores, EQ-5D-5L, PROMIS 13a and Fatigue Items, PROMIS interest in sexual activity, PGIS, and PGIC.

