2.2.2 Randomization and Blinding

2.2.2.1 Randomization

Patients who meet all inclusion criteria and no exclusion criteria will be randomized to one of three dose levels of Ziltivekimab (7.5 mg, 15 mg or 30 mg) or placebo for a 24 Week Treatment Period. Treatments will be assigned to randomized patients via an Interactive Web-Response System (IWRS). 240 patients will be randomized in a 1:1:1:1 ratio (60 per group) to Ziltivekimab 7.5 mg, Ziltivekimab 15 mg, Ziltivekimab 30 mg, or matching Placebo. Patients will be stratified

by baseline hemoglobin (≥ 11 or < 11 g/dL) and CKD stage (3, 4 or 5). Note that CKD stage is stratified into two categories: (1) stage 3 and (2) stages 4 and 5.

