3.4 Efficacy Assessment

For all efficacy variables, the number of patients (n), mean, standard deviation (SD), median, quartiles (Q1 and Q3), minimum (min) and maximum (max) values for the observed value, change from baseline, and percent change from baseline (as applicable) will be reported. The difference (Ziltivekimab - Placebo) in changes or percent changes (as applicable) will be presented.

A mixed model for repeated measures (MMRM) will be used to evaluate change (or percent change) from baseline. The model will include variables for baseline hemoglobin (≥ 11 or < 11 g/dL), CKD Stage (3, 4 or 5), treatment group, visit and treatment group-by-visit interaction as categorical fixed effects, baseline value and baseline-by-visit interaction will be included as covariates. The least squares means for each dose, the least squares mean differences from placebo along with the associated 95% confidence intervals (CIs) and p-values will be presented. If the normality assumption is not met, a nonparametric test will be selected for efficacy analysis.

An unstructured covariance matrix will be used to model the within-subject correlation. The Kenward-Roger approximation will be used to adjust the denominator degrees of freedom. The analysis will be performed based on all observed post-baseline scores without any imputation of missing data. In the case when the MMRM fails to converge using an unstructured covariance matrix in any stage, a less stringent covariance matrix (e.g., autoregressive 1) will be used.

Sensitivity analyses will be conducted to explore the robustness of the result for primary efficacy endpoint based on MMRM. Efficacy data will be summarized by randomized treatment group based on the ITT and PP analysis populations.

The differences in proportions and 95% CIs will be based on the normal approximation to binomials.

Missing data will be imputed only in the context of sensitivity analysis as described in section 3.4.1.

The pharmacodynamic efficacy of three Ziltivekimab doses compared to placebo will be assessed by evaluating the following:

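### The plan promises differences in hs-CRP responder proportions with 95% CIs, but its sample code returns only one-arm proportions and limits, with no difference from placebo

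*SAP*

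**What the plan says.** SAP section 3.4 (Efficacy Assessment) sets the general rule for binary endpoints: "The differences in proportions and 95% CIs will be based on the normal approximation to binomials". Section 3.4.3 repeats it and introduces the code as its implementation: "The sample SAS code for normal approximation for binary endpoints can be found below".

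That code is a PROC FREQ step with a `by TRT` statement. It has a one-way table request, "tables ACHIEVE / binomial (Wald exact", and an output statement, "ods output BinomialCLs=CL BinomialProp=Proportion".

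The endpoint it serves is listed in the same section as "Proportion of patients achieving hs-CRP response at Week 13 and to End of Treatment (Weeks 23 through 24"), with response "defined as hs-CRP <2.0 mg/L in each active group and placebo".

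Section 2.2.2.1 gives the planned size: "240 patients will be randomized in a 1:1:1:1 ratio (60 per group"). The same section says that randomisation was stratified by baseline hemoglobin and by CKD stage in two categories, 3 and 4/5.

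**The concern.** A programmer who follows the code delivers four separate proportions, each with its own limits. The quantity that the text promises, the difference between each dose and placebo with its interval, is not among the output. The programmer must then depart from the printed code or add a step that the plan does not describe. The interval for the difference would be settled at programming stage rather than in the plan.

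A second question is whether a normal-approximation interval is a sound choice. It is known to behave poorly when a proportion is near 0 or 1, and a threshold response to a strong anti-inflammatory agent might produce such rates.

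Section 2.1 says that the trial is meant to help select a dose for a possible outcome trial. A responder difference would be a natural summary to look at, although the SAP does not make it a selection criterion.

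**Working it through.** **1. Text against code.** The text asks for a two-sample quantity, p1 − p2, with a 95% CI. The code stratifies the run by treatment, tabulates the response alone and saves only one-sample output. It contains no treatment-by-response table and no risk-difference request. No statement in it can produce p1 − p2. The request in brackets asks for exact limits as well as Wald limits, so each arm gets both.

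**2. Illustration** (counts invented for the purpose): 40/60 on a dose, 6/60 on placebo.
- Output of the code, Wald, p ± 1.96·√[p(1−p)/n]: 0.667 (0.547 to 0.786) and 0.100 (0.024 to 0.176), plus exact limits for each arm.
- Output that the text promises: 0.667 − 0.100 = 0.567, with standard error √[0.667·0.333/60 + 0.100·0.900/60] = 0.0721. The 95% CI is 0.567 ± 1.96·0.0721, that is 0.425 to 0.708.
- Newcombe interval for the same data: 0.405 to 0.685.

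**3. Does the normal approximation matter here?** The SAP gives no expected responder rate, so every rate below is an assumption. The sample sizes have a source. Section 2.2.4 gives 54 evaluable and 60 randomised per group, consistent with 54/(1 − 0.10) = 60. Section 5 reports about 140 completers and more than 120 non-completers, so more than 260/4 = 65 per group; I used 66 as the upper value.

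For each pair of true rates, coverage was found by enumerating all outcomes of two independent binomials and summing the probability of those whose nominal 95% interval contains the true difference. Rates were stepped by 1 percentage point, with equal arms and no stratification.

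*Extreme rates (placebo 2-10%, active 80-98%):*

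| n per arm | Wald mean | Wald min | Newcombe mean | Newcombe min |
|---|---|---|---|---|
| 54 | 0.922 | 0.833 | 0.945 | 0.922 |
| 60 | 0.925 | 0.801 | 0.948 | 0.910 |
| 66 | 0.930 | 0.839 | 0.948 | 0.927 |

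Wald coverage is below 0.93 at 53%, 43% and 42% of these points; Newcombe at 6%, 2% and 1%.

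*Wider rates (placebo 2-30%, active 30-95%):* Wald mean 0.941, 0.942 and 0.943 at 54, 60 and 66 per arm; Newcombe mean 0.949 to 0.950. The average Wald loss is therefore about 0.95 − 0.94 = 1 point. Its low values again occur where both rates are extreme.

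**4. The one-arm limits that the code does print.** At n = 60, Wald coverage is 0.701 at a true rate of 2%, 0.806 at 5% or 95%, and 0.941 at 10% or 90%. The exact limits cover at least 0.96 at every rate tested (2% to 95%, n = 54 and 60).

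**The case against.** The strongest defence is that the prose governs and the code is labelled a sample. The Wald interval for a difference can be rebuilt from what the code saves. In the illustration the one-arm half-widths are 0.1193 and 0.0759, √(0.1193² + 0.0759²) = 0.141, and 0.567 ± 0.141 is the interval in step 2 (to rounding). The endpoint bullet also speaks of a proportion in each group, which per-arm output does serve. All of this is correct. A reader who infers that the between-arm comparison is lost goes too far. What remains is that two sentences promise differences, the code is presented as their implementation, and the step from one to the other is not written down.

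A reader might also infer that the planned intervals under-cover at the rates expected. The documents do not support that. The assumed effect in section 2.2.4 is a difference of −60.74 points in mean percent change, which is not a responder rate. If placebo did not change (an assumption), a fall of 60.74% would reach 2.0 mg/L only from a baseline of 2.0/(1 − 0.6074) = 5.1 mg/L or less, and the SAP gives no baseline distribution. Nor are all the printed limits too narrow, since exact limits are requested beside the Wald ones.

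Finally, nothing in sections 3.4 or 3.4.3 promises a stratified binary analysis, so its absence is not a contradiction. The case for one is consistency: the MMRM, the aligned rank analysis (both section 3.4.1) and the ANCOVA (section 5) all use hemoglobin category and CKD stage. With four strata and about 60 per arm some cells could be sparse. The coverage of a stratified Newcombe interval was not examined here.

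**Conclusion.** The mismatch is established by the text alone: sections 3.4 and 3.4.3 promise differences in proportions with 95% CIs, and the code in 3.4.3 returns one-arm proportions with Wald and exact limits and no difference from placebo.

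The preference for a score-type interval is conditional. If one or both rates lie near 0 or 1, it recovers roughly 2 points of average coverage and avoids the worst Wald values. At moderate rates the gain is about 1 point or less. These figures rest on assumed rates, equal arms of 54 to 66 and an unstratified comparison.

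The impact is limited. The endpoint is exploratory and lies outside the sequential testing procedure of section 3.4.4, which covers only the primary endpoint.

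**What to change.** In section 3.4.3, replace the sample code. For each dose in turn, restrict the data to that dose and placebo, drop the `by TRT` statement, request a two-way `TRT*ACHIEVE` table with the risk difference for response = yes, and save the risk-difference output. Name one score-type 95% CI (Newcombe or Miettinen-Nurminen) in place of Wald. State the direction as ziltivekimab minus placebo, as section 3.4 does for the other efficacy differences. Amend the sentences in 3.4 and 3.4.3 to name the same interval. Check the option syntax against the SAS release in use, since section 6 allows 9.3 or higher. Keep the per-arm proportions with exact limits as description.

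Where stratum counts allow, add a risk difference stratified by hemoglobin category and CKD stage as randomised (3 against 4/5), alongside the unstratified result and not as its sole replacement.

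The cost is a few lines of code and one sentence in each of the two sections. No new data are needed.
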